**Table 5-2 Dosing adjustment of study drug administration in the event of treatment-emergent systolic BP decrease**

Changes in systolic BP during infusion*	Adjustments of study drug administration
Decrease >40 mmHg from pre-treatment at baseline, but systolic BP remains $\geq 100$ mmHg	Reduce the infusion rate by half for the remainder of the study drug administration, i.e., reduce infusion rate from 10 mL/hour to 5 mL/hour for the remainder of 48-hour infusion
Decrease in absolute systolic BP to $<100$ mmHg	Permanently terminate study drug infusion

\* These systolic BP values should be confirmed by two measurements taken 15 minutes apart

In addition, dosing may be discontinued at any time at the discretion of the investigator.

Reasons the investigator may discontinue study drug administration include, but are not limited to, serious or intolerable AEs suspected to be related to study drug. If dosing is discontinued for hypotension or any safety reasons, re-administration of study drug is not allowed. For non-safety reasons (problems with the infusion line, etc.), dosing may be interrupted once for each patient in general for up to 1 hour in each 24-hour infusion period. If the infusion is stopped for longer than 1 hour, the infusion should still be allowed to continue as long as it is safe for the patient. This time is not to be added back to the end of the infusion and the timed protocol assessments are not to be adjusted. Time from initiation of study drug infusion to completion must not exceed 48 hours. In the event that study drug administration is discontinued for any reason, the patient will continue to be followed at all study visits defined in the protocol.

These changes must be recorded on the Dosage Administration Record CRF.

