#### **6.6.2      Pharmacokinetics**

##### **Blood sample collection and processing**

Blood samples for PK will be taken at baseline, 48 hr and Day 60. The 48 hr PK sample should be taken prior to the end of infusion. If the infusion was discontinued earlier than the complete 48 hr infusion due to whatever the reason, the 48 hr PK serum sample will be collected just prior to the end of infusion if possible and time of collection should be recorded. The PK samples at baseline and Day 60 are collected as a part of immunogenicity analysis package.

[figure not shown]
Blood sample will be taken by either direct venipuncture or an indwelling cannula inserted in a forearm vein contra-lateral to the site of the infusion. If an indwelling cannula is used, a 0.5 mL discard will be taken before the PK sample in case the indwelling cannula was flushed with saline. Serum separator tubes will be used to collect serum for the determination of serelaxin concentrations

For pharmacokinetic analysis of serelaxin, approximately 2 mL blood will be drawn into a serum separator tube. Instructions regarding the sample collection and handling including clotting time, centrifuge temperature and duration, storage and shipment are described in the Laboratory Manual.

All samples will be given a unique sample number (as listed in [Appendix 6](#)). The first aliquots should be sent to the bioanalytical center on dry ice, while the back-up aliquots should be sent to the same address after assurance that the first aliquots arrived in good condition. For detailed instructions on labeling and shipment of samples, please refer to the Laboratory Manual.

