### **9.5.5 Pharmacokinetics**

Steady state concentration (Css) will be estimated based on the serum concentration determined at the 48 hr time point prior to the end of infusion. Systemic clearance will be calculated using the rate of infusion and Css for each patient as indicated below:

$$\text{Clearance (mL/hr/kg)} = \text{Rate of infusion (\mu g/kg/hr)} / \text{Css (\mu g/mL)}.$$

Since only sparse PK time points for serelaxin serum concentration will be collected, no other PK parameters will be determined in this study.

Concentrations below the assay LLOQ (BLQ) will be treated as zero for PK parameter calculations.

Descriptive statistics for serelaxin concentrations will be listed by time points (for baseline and 48hr samples only) to include arithmetic mean, geometric mean with its corresponding 90% confidence interval, median, SD, CV, min and max. A value of "0" will be used for samples that are BLQ in these calculations and therefore be excluded from geometric mean calculations. Descriptive statistics include arithmetic mean, geometric mean with its corresponding 90% confidence interval, median, SD, CV, min and max will also be provided for the two PK parameters, Css and clearance.

Subgroup analysis on Css and CL to assess the potential effects of various extrinsic and intrinsic factors on the PK of serelaxin may be performed as appropriate. These factors may include but not limited to age, gender, race, country of origin, concomitant medications, etc. Details of these analyses will be described in the Statistical Analysis Plan.

Serelaxin serum concentration will be assayed in Day 60 samples as well, in order to demonstrate the lack of drug interference with the immunogenicity assay, but this data will be included only as part of the immunogenicity results but not in the PK results.

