## 18 Appendix 6: Blood collection log for PK and immunogenicity samples

Study Phase	Visit No.	Study Day	Time post start of infusion (hr)	PK			IG		Total Volume
				Sample Size (mL)	Sample No.	Dose Ref. ID	Size (mL)	Sample No.	
Baseline	101	D1	0 (Pre)	2	101	1	3	201	5
Treatment	105	D2	48*	2	102	1	--	--	2
Follow-up	110	D60	1440	2	103	1	3	202	5

\* 48hr sample taken prior to the end of infusion. . If the infusion was discontinued earlier than the complete 48 hour infusion due to whatever the reason, the 48 hour PK serum sample will be collected just prior to the end of infusion if possible and time of collection should be recorded.

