2.1.3 Time window, baseline and post-baseline definitions, and missing data handling

Screening phase (Hour -16): The screening phase is the time period prior to randomization, which should be within 16 hours after presentation. After obtaining written informed consent, the subject will be evaluated for eligibility to participate in to the study.

All references to index hospitalization refer to the initial hospitalization for acute heart failure (AHF).

Baseline (Hour 0/Day 1): The assessments identified in the eCRF as baseline assessments will be used as the baseline reference for all analyses. The baseline date and time will be considered the date and time of initiation of study drug, or randomization if the subject was not treated with study drug. If the value is missing, the last value at screening visit will be used.

Post-baseline phase: The post-baseline phase begins at the time when study drug administration starts (Hour 0/Day 1) and ends with the last study assessment/last follow-up or the death of subject. For subjects who did not receive study drug, the post-baseline phase begins at time of randomization.

Time window: For the scheduled post-baseline visits, time window is not defined; the data will be used as reported in eCRFs (i.e., the actual assessment times will not be used to

[figure not shown]
reclassify the time point at which a measure was taken). The by-visit report will be presented by protocol scheduled visit. Time-to-event analyses will be based on actual date and time as reported when available.

Missing data handling

Missing data handling for efficacy endpoints are discussed in [Section 2.2](#), Efficacy evaluation. In general, missing values of other assessment/measurement will not be imputed unless otherwise specified.

The dates for efficacy endpoint events and AE events should be reported as instructed in eCRFs. If a partially missing date cannot be resolved after data query, the following is the general rule for imputation as necessary only if the calculation is needed (e.g., to calculate time-to-event):

- a) if only the month of the event is known, then the 15th day of this month will be imputed for a missing day in case the month and year are after the month and year of double blind treatment start. If the month and year are equal to the double blind treatment start then the event date will be imputed by the treatment start date.

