2.3 Pharmacokinetic evaluations

All subjects with at least one available valid (i.e. not flagged for exclusion) PK concentration measurement, who received serelaxin infusion and experienced no protocol deviations with relevant impact on PK data will be included in the pharmacokinetic (PK) data analysis. Steady state concentration (Css) will be estimated based on the serum concentration determined at the 48 hour time point prior to the end of infusion. Systemic clearance will be calculated using the rate of infusion and Css for each subject as indicated below:

$$\text{Clearance (mL/hr/kg)} = \text{Rate of infusion (\mu g/kg/hr)} / \text{Css (\mu g/mL)}$$

Where the rate of infusion is the actual dosing rate calculated as below for each individual subject:

$$\text{Rate} = \frac{\text{VolRLX}}{\text{VolRLX} + \text{VolSol}} \times \frac{\text{ConcRLX}}{\mu\text{g/mL}} \times \frac{\text{Flow}}{\text{mL/hr}} \times \frac{24}{\text{hrs/day}} / \frac{\text{Weight}}{\text{kg}}$$

where VolRLX is the volume of serelaxin drawn from the vials and added to a volume VolSol of the solution contained in the infusion bag, ConRLX is the concentration of the serelaxin stock solution in the vial (1000 $\mu\text{g/mL}$), Flow is the flow rate of the solution from the infusion bag, and Weight is the body weight measured at Day 1 pre-dose baseline. Since only sparse PK time points for serelaxin serum concentration will be collected, no other PK parameters will be determined in this study.

Missing values or those below the assay LLOQ (BLQ) will be indicated in the data listings and treated as zero for PK parameter calculations and presentation.

Descriptive statistics for serelaxin concentrations will be listed by time points (for baseline and 48hr samples only) to include arithmetic mean, geometric mean with its corresponding 90% confidence interval, median, SD, CV, min and max. A value of "0" will be used for samples that are BLQ in these calculations and therefore be excluded from geometric mean calculations. Descriptive statistics include arithmetic mean, geometric mean with its corresponding 90% confidence interval, median, SD, CV, min and max will also be provided for the two PK parameters, Css and clearance (CL).

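### Css and clearance come from the nominal 48 h PK sample with no minimum time on an unchanged infusion rate, so samples from early stops or soon after a rate change can enter as steady state

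*SAP*

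**What the plan says.** Protocol 9.5.5 takes Css from one sample: "Steady state concentration (Css) will be estimated based on the serum concentration determined at the 48 hr time point prior to the end of infusion". SAP 2.3 repeats this ("Steady state concentration (Css) will be estimated based on the serum concentration determined at the 48 hour time point"), sets clearance equal to rate of infusion divided by Css, and defines the rate as each subject's actual dosing rate. One input to that rate is the flow from the infusion bag.

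The 48 h label does not guarantee 48 h of infusion. If the infusion ends early, protocol 6.6.2 directs that "the 48 hr PK serum sample will be collected just prior to the end of infusion if possible", with the collection time recorded. The blood log in Appendix 6 carries the sample as number 102, Visit 105, 48 h, with a footnote that begins "If the infusion was discontinued earlier than the complete 48 hour infusion due to whatever the reason".

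The rate can also change. For a confirmed systolic fall of more than 40 mmHg with pressure still at or above 100 mmHg, protocol Table 5-2 says "Reduce the infusion rate by half for the remainder of the study drug administration", that is, from 10 to 5 mL/h. For a confirmed value below 100 mmHg it ends the infusion. Protocol 6.5.2 schedules pressure checks from 30 minutes, so either can happen within hours of the start. Protocol 5.5.5 also allows interruptions for non-safety reasons.

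SAP 2.3 admits subjects with at least one "available valid (i.e. not flagged for exclusion) PK concentration measurement" who received serelaxin and had no protocol deviation relevant to PK. It gives no criteria for the flag. For scheduled visits in general, SAP 2.1.3 says that "the actual assessment times will not be used to" move a measurement to another time point.

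**The concern.** Rate divided by concentration equals clearance only once concentration has settled at a constant rate. A sample drawn just before an early stop may still be on the rising part of the curve. A sample drawn soon after a halving still carries drug from the higher rate. Applied as written, the rule calls both Css and divides them into a rate.

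Neither of the SAP's filters clearly prevents this. A stop or halving that the protocol requires is not a deviation, and the flag is left to unstated judgement. The flow term adds an ambiguity, because the SAP does not say whether the initial or the current rate applies after a change.

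At stake are the Css and clearance summaries and any subgroup comparison of them by renal function, age, country or co-medication, which the SAP says may be performed.

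**Working it through.** **Inputs.** The documents state no Css, clearance, half-life or number of early stops, so there is no planned figure to reproduce. Taken from the documents: a 48 h infusion, 10 mL/h, 5 mL/h after a halving (protocol 5.5.4 and Table 5-2), and clearance = rate/Css (SAP 2.3). Assumed: one compartment and a half-life *h* of 1, 2, 6 or 12 h. Protocol 1.1 mentions half-life data from healthy volunteers but gives no value.

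**Step 1, early stop at t hours.** Concentration is Css × (1 − 2^(−t/h)). Using it as Css gives apparent/true clearance = 1/(1 − 2^(−t/h)). For a stop at 6 h: h = 1 gives 1/(1 − 1/64) = 1.02; h = 6 gives 1/(1 − 0.5) = 2.00; h = 12 gives 1/(1 − 0.707) = 3.41.

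| Draw at stop | h = 1 | h = 2 | h = 6 | h = 12 |
|---|---|---|---|---|
| 1 h | 2.00 | 3.41 | 9.17 | 17.8 |
| 3 h | 1.14 | 1.55 | 3.41 | 6.29 |
| 6 h | 1.02 | 1.14 | 2.00 | 3.41 |
| 12 h | 1.00 | 1.02 | 1.33 | 2.00 |
| 24 h | 1.00 | 1.00 | 1.07 | 1.33 |
| 48 h (full infusion) | 1.00 | 1.00 | 1.00 | 1.07 |

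**Step 2, halving s hours before the draw, after steady state at 10 mL/h.** Concentration is the new Css × (1 + 2^(−s/h)). Apparent/true clearance is 1/(1 + 2^(−s/h)) if flow is the 5 mL/h in force, and 2/(1 + 2^(−s/h)) if flow is the initial 10 mL/h.

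| Draw after halving | Flow used | h = 1 | h = 2 | h = 6 | h = 12 |
|---|---|---|---|---|---|
| 1 h | 5 | 0.67 | 0.59 | 0.53 | 0.51 |
| 1 h | 10 | 1.33 | 1.17 | 1.06 | 1.03 |
| 6 h | 5 | 0.98 | 0.89 | 0.67 | 0.59 |
| 6 h | 10 | 1.97 | 1.78 | 1.33 | 1.17 |
| 24 h | 5 | 1.00 | 1.00 | 0.94 | 0.80 |
| 24 h | 10 | 2.00 | 2.00 | 1.88 | 1.60 |

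With the current flow the error fades as time passes. With the initial flow it grows towards 2-fold.

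**Step 3, both together.** For a halving at 3 h and a stop at 6 h, concentration relative to the full-rate Css is (1 − 2^(−3/h)) × 2^(−3/h) + 0.5 × (1 − 2^(−3/h)). Dividing 0.5 by this gives 0.91, 0.91, 1.41 and 2.34 for h = 1, 2, 6 and 12. The two errors pull in opposite directions, so no single correction factor would serve.

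**Step 4, effect of a minimum time.** At 4 half-lives after the start the ratio is 1/(1 − 1/16) = 1.07; at 4 half-lives after a halving, with the current flow, it is 1/(1 + 1/16) = 0.94. At 5 half-lives the values are 1.03 and 0.97.

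**The case against.** The best reply is that SAP 2.3 already has a sample-level filter, separate from protocol deviations, and that collection times, infusion times and rates are all recorded. A PK analyst could flag every unsuitable sample. The general visit rule in SAP 2.1.3 stops relabelling of visits; it does not forbid flagging. This stands in part. A reader might infer that every sample logged as 48 h must enter as Css, and the documents do not go that far. But a flag without criteria does not amend the stated rule, and the choice is left until concentrations are in hand.

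Second, clearance uses the actual dosing rate, so halving is largely handled when it comes well before a true 48 h draw. This also stands, provided flow means the rate at the draw. The inference that clearance is distorted in all patients whose pressure fell is therefore not supported. Early stops for other reasons and line interruptions raise the same problem, so it is not confined to those patients either.

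Third, the size depends on a half-life, stop times and stop frequencies that the documents do not give. With a 1 h half-life, a stop at 6 h is harmless. This stands, and it rules out putting a figure on any spurious subgroup difference, because nothing shows how stops would divide across subgroups. Nor do the documents provide for a draw after the infusion has ended.

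Finally, a reader might infer that the case for this regimen in Asian patients is weakened. Protocol 3.3 rests that case on RELAX-AHF and on a PK study showing no ethnic sensitivity, not on Css from this trial. PK is not among the objectives in protocol section 2.

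**Conclusion.** The rule as written is faulty, not merely brief: it assigns steady-state status by sample label rather than by infusion history. Under a one-compartment model, a stop at 6 h gives apparent clearance of about 1.02 to 3.4 times the true value for assumed half-lives of 1 to 12 h, and earlier stops give more. A draw 1 h after a halving gives 0.67 to 0.51 times true clearance with the current flow. Carrying the initial 10 mL/h forward overstates it by up to 2-fold. Patients with a full 48 h at constant rate are within about 7%, and those halved well before a true 48 h draw are not materially affected if the current flow is used.

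The mechanism is certain; the size in this trial is not, because it turns on the half-life and on how many infusions stop or change early. The effect is confined to descriptive Css and clearance summaries and optional PK subgroups. Efficacy and safety conclusions are untouched.

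**What to change.** In SAP 2.3 and protocol 9.5.5:

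- Derive Css and clearance only from samples whose recorded time falls during the infusion and at least a pre-set 4 to 5 half-lives after the start or the last rate change or interruption. Take the half-life from the sponsor's own PK data and state the resulting hours.
- Make this the written criterion behind the exclusion flag.
- Define flow as the rate in force at the draw.
- List every other nominal 48 h concentration with its actual time and rate history, without deriving Css or clearance.

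The cost is a wording change and a filter on sample time and the dosing record, both already collected. No dosing or stopping rule changes. The drawback is fewer patients in the summaries, which then describe those on a constant-rate infusion; the text accompanying the tables should say so. If the half-life were as long as 12 h, 4 half-lives would be 48 h and only completed, unchanged infusions would qualify.

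### SAP 2.3 feeds a per-day infusion rate into a per-hour clearance formula, making clearance 24 times too large as printed; it also sets missing values to zero, which the protocol does not

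*SAP*

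**What the plan says.** **Clearance and its rate.** Protocol 9.5.5 and SAP 2.3 give the same clearance formula: a rate in µg/kg/hr over Css in µg/mL, with the result in mL/hr/kg. The protocol does not say how to compute the rate. SAP 2.3 does: "Where the rate of infusion is the actual dosing rate calculated as below for each individual subject". Its formula takes the drug's share of the total bag volume, multiplies by the stock concentration (1000 µg/mL), by the flow in mL/hr and by 24 hrs/day, and divides by body weight in kg.

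**Missing and BLQ values.** Protocol 9.5.5 sets concentrations below the LLOQ to zero for PK parameters and does not mention missing ones. SAP 2.3 goes further: "Missing values or those below the assay LLOQ (BLQ) will be indicated in the data listings and treated as zero for PK parameter calculations". Its next paragraph, on concentration summaries, says only that a zero "will be used for samples that are BLQ in these calculations", with BLQ as the sole case.

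**Who is analysed.** SAP 2.3 admits "All subjects with at least one available valid (i.e. not flagged for exclusion) PK concentration measurement", provided they received serelaxin and "experienced no protocol deviations with relevant impact on PK data will be included in the pharmacokinetic (PK) data analysis". Css "will be estimated based on the serum concentration determined at the 48 hour time point". Under protocol 6.6.2, after an early stop that sample is drawn just before the infusion ends, where this is possible.

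**The concern.** The SAP is the programming specification. It ties the two formulas together explicitly, yet the second delivers a daily quantity to a first that is labelled hourly. A programmer who follows both as printed reports clearance in the wrong unit under the right label. Css and clearance are the only PK parameters the trial will produce, so half of the parameter output is exposed: mean, geometric mean with its interval, median, SD, minimum and maximum.

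The missing-value sentence raises a separate problem. A serelaxin patient with a valid baseline sample but no 48-hour sample can meet the one-valid-concentration condition. The documents do not say whether a missing 48-hour sample is a deviation with relevant impact on PK: SAP Table 2-1 covers only RAN, FAS, SAF and PPS and lists no missing PK sample. Read literally, such a patient has Css = 0 and clearance = rate/0.

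**Working it through.** The documents state no numerical clearance, so there is no figure of the plan's own to reproduce. The check is a unit analysis followed by evaluation of the printed formula.

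**Inputs**
- Drug volumes by weight band: 1.5, 2.0, 3.0, 3.5 and 5.5 mL (protocol Table 5-1)
- Bag volume 250 mL and flow 10 mL/hr (protocol 5.5.4); reduced flow 5 mL/hr (protocol Table 5-2)
- Stock concentration 1000 µg/mL (SAP 2.3)
- Nominal dose 30 µg/kg/day (protocol 5.1.1), that is 30/24 = 1.25 µg/kg/hr
- Taken here: VolSol = 250 mL exactly

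**Units**

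(mL/mL) × (µg/mL) × (mL/hr) × (hr/day) / kg = µg/kg/day.

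Dividing by Css in µg/mL gives mL/day/kg, not mL/hr/kg. The ratio is 24.

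**Values at 10 mL/hr**

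Rate as printed = V/(V + 250) × 1000 × 10 × 24 / weight. The hourly rate is the same without the 24.

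- 30 kg: 1.5/251.5 × 1000 × 10 × 24 / 30 = 47.71 µg/kg/day; hourly 1.988 µg/kg/hr
- 114 kg: 3.5/253.5 × 1000 × 10 × 24 / 114 = 29.07 µg/kg/day; hourly 1.211 µg/kg/hr

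These are the highest and lowest values over the ends of the five bands as tabulated. At 5 mL/hr they become 23.86 (hourly 0.994) and 14.53 (hourly 0.606). The ratio is 24 in every band and at both flows, because it depends on neither weight, flow nor Css. The printed results lie on the scale of the nominal 30 µg/kg/day, which confirms that the formula is per day.

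**Effect on clearance at the nominal dose.** The documents give no Css, so assume 0.005 to 0.020 µg/mL for illustration:
- With the hourly rate: 1.25/0.005 = 250, down to 1.25/0.020 = 62.5 mL/hr/kg
- As printed: 30/0.005 = 6000, down to 30/0.020 = 1500, under the same label

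**Missing set to zero.** If a share p of 48-hour values is zero-filled, and missingness is unrelated to level, the arithmetic mean of Css becomes (1 − p) × its true value. The documents give no missing rate. As assumed examples:
- p = 0.05 gives 0.95 of the true mean
- p = 0.10 gives 0.90 of the true mean; with 1,520/2 = 760 serelaxin patients all in the PK set, that is 76 patients

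Clearance for these patients is rate/0, which is undefined. The same holds for a BLQ 48-hour value under both documents.

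**The case against.** **On the units.** Both documents label the clearance input as hourly, and the 24 carries its own hours-per-day label, so a careful programmer would see the mismatch and divide by 24. The rate formula may simply be the daily dosing rate with one conversion step left unsaid. The rate also appears without a unit in the text as read from PDF, and one could have been lost in reading. It stands that a unit check would reveal the error. But the 24 and its label are legible, the SAP says this formula is the rate to be used, and no step converts it. A lost label on the rate would not supply that step.

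**On missing values.** The protocol is silent on missing concentrations, so the SAP adds a rule rather than contradicting one. Css needs a concentration that was determined at 48 hours, so without a sample there may be no Css at all. SAP 2.1.3 leaves other missing measurements unimputed by default, and early stopping alone does not make the sample missing, since one may be drawn at the end of infusion. This makes the zero-filled reading uncertain. It does not remove it: the SAP 2.1.3 default gives way where something else is specified, and the SAP 2.3 sentence can be read as exactly that.

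**On size.** The proportional fall applies only to the arithmetic mean. A zero cannot enter a geometric mean, and the median does not fall by the missing share. The range of rates uses whole-kilogram band limits; if 114.9 kg were dosed in the 75–114 kg band, the lowest printed value would be 28.8 rather than 29.1. The factor of 24 would be unchanged.

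**Conclusion.** The unit error is certain as the SAP is printed: clearance programmed from these two formulas is 24 times too large for its stated unit in every patient. Being a constant multiple, it leaves the CV of clearance and clearance ratios between subgroups unchanged, and Css does not use it.

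The missing-value wording is a real inconsistency with the protocol's BLQ-only rule and with the SAP's own summary sentence, but its effect depends on how it is read and on a missing rate that the documents do not give. Unlike the factor 24, zero-filling would not cancel in the Css subgroup comparisons if missingness differed between subgroups.

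The point is minor overall. It concerns descriptive PK only, and no efficacy test depends on it.

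**What to change.** In SAP 2.3:
- Remove the 24 from the rate formula, or divide the rate by 24 before computing clearance, and print the unit beside the rate.
- State that a missing 48-hour concentration stays missing and is excluded from Css and clearance.
- Keep BLQ = 0 for concentration summaries, and report clearance as not calculable when the 48-hour value is missing or BLQ.

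It would also help, though it is optional, to give n for each PK statistic and to say whether a missing 48-hour sample counts as a PK-relevant deviation.

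The cost is SAP wording and PK programming. No trial procedure or data collection changes.
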